2.0 Clinical study

The trial will be conducted in compliance with the protocol, GCP and the applicable regulatory requirement(s).

Trial Objectives and Purpose

The main objectives of the research study is to evaluate the safety, efficacy and costeffectiveness of a bio-inspired artificial pancreas (BiAP) with, and without, the addition of an adaptive bolus calculator (ABC4D) compared to gold-standard sensor-augmented pump therapy.

Hypothesis

- 1. A bio-inspired artificial pancreas (BiAP) device has a positive impact on glucose control, as measured by time in target after 6 weeks of use, when compared with sensor-augmented pump with low-glucose suspend (LGS).
- 2. A bio-inspired artificial pancreas (BiAP) device with an adaptive bolus controller (ABC4D) has an additional positive impact on post-prandial glucose control.

Trial Design

A 3-way crossover randomized controlled trial (Fig 3). Description of the three arms:

- 1. Sensor augmented pump (open-loop)
- 2. BiAP with a fixed bolus calculator
- 3. BiAP with the Advanced Bolus Calculator for Diabetes (ABC4D)

The primary outcome from the studies will be % time spent with a glucose concentration in the target range (3.9-10.0mmol/l). This outcome incorporates safety as it ensures participants do not have low or high glucose excursions and is the principal measure of efficacy for closed-loop insulin delivery systems in the scientific literature. Other measured outcomes will be % time spent in euglycaemia (3.9-7.8mmol/l), % time spent in hypoglycaemia (<3.9mmol/l), % time spent in hyperglycaemia (>10mmol/l), mean venous blood and sensor glucose, glycaemic variability as measured by standard metrics (SD, CONGA, LI, JINDEX, GRADE, MODD, MAGE, ADDR, MVALUE, MAG), glycaemic risk as measured by low blood glucose index (LBGI) and high blood glucose index (HBGI), closed-loop error grid analysis, glucose area under the curve. All measures have been previously published and validated. Quality of life, treatment satisfaction and device acceptability outcomes will be measured using mixed methods (questionnaires and semi-structured interviews).

Methodology Randomised controlled cross-over open label study

Timescale It is anticipated that the study will take 1 year, each subject will be in the study for up 6 months, with a total of 6 visits in that timeframe.

Population

n = 20

Inclusion criteria

- Adults over 18 years of age

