3.0 Statistics

From our previous published data^{1,6} we anticipate that the BiAP/ABC4D intervention will increase the percentage of time for which plasma glucose concentrations were in the target range by a mean of 6% (SD 9.9) compared with the BiAP/fixed bolus artificial pancreas system, and by an estimated mean of more than 6% (9.9) compared with the control group. We intend to do three pairwise comparisons between the interventions, and therefore have conducted a power analysis using the typical sample size formula for the paired t test. We estimate, using mean 12% (9.9), that 20 participants would provide 90% power at the 5% significance level (corrected for multiple comparisons) to detect differences between the three interventions.

Missing, unused, and spurious data will be assessed on an individual basis and may be ignored, withdrawn or the visit may be removed from the analysis with appropriate justification adjudicated by the Principal Investigator.

Efficacy

Primary outcome will be:

• % time in target range defined as 3.9-10mmol/l

Secondary outcomes will be:

- % time spent in euglycaemia (3.9-7.8mmol/l)
- % time spent in hypoglycaemia (<3.9mmol/l)
- % time spent in hypoglycaemia (<2.8mmol/l)

- % time spent in hyperglycaemia (>10mmol/l)
- % time spent in severe hyperglycaemia (<15mmol/l)
- Mean sensor glucose
- Glycaemic variability
- Glycaemic risk as measured by LBGI and HBGI
- Closed loop error grid analysis
- Glucose area under the curve
- Insulin requirement in units/kg/hr
- Hypoglycaemia awareness (Gold scores)
- Quality of life by mixed quantitative and qualitative methodologies
- Cost-effectiveness
- Device usability and acceptability
- % time in closed loop control
- Severe hypoglycaemia
- Diabetic ketoacidosis
- Sensor MAD%

These are validated, published metrics, which will be assessed at the end of each visit from CGM data. There will be an interim analysis of the data after each visit to ensure efficacy and safety.

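### The secondary outcome for severe hyperglycaemia is defined as glucose below 15 mmol/l; computed as written, its direction of benefit is reversed

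*Combined protocol and SAP*

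**What the plan says.** Section 3.0 Statistics defines the outcomes through a set of glucose ranges. The primary outcome is "time in target range defined as 3.9-10mmol/l". The secondary list gives "time spent in euglycaemia (3.9-7.8mmol/l"), then "time spent in hypoglycaemia (<3.9mmol/l") and "time spent in hypoglycaemia (<2.8mmol/l"), then "time spent in hyperglycaemia (>10mmol/l"), and directly after that "time spent in severe hyperglycaemia (<15mmol/l").

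The only other list of outcomes is under Trial Design in Section 2.0. It runs from "time spent in hyperglycaemia (>10mmol/l), mean venous blood and sensor glucose" on to the variability and risk indices, and it has no item for severe hyperglycaemia. Section 3.0 is the only statistics section in this combined document, and the 15 mmol/l figure appears as a glucose threshold nowhere else.

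**The concern.** Severe hyperglycaemia has to be a subset of hyperglycaemia. The plan sets hyperglycaemia above 10 mmol/l and then sets the severe category below 15 mmol/l, a range made up mostly of normal and low glucose. The label and the threshold cannot both be right.

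If the definition were coded literally, the outcome would move against its own name: the better an arm is at avoiding very high glucose, the more severe hyperglycaemia it would appear to have. This could matter during the trial as well as at the end. Section 3.0 says the metrics are assessed after each visit and feed an interim look at efficacy and safety, and Section 6.0 (Study Management) has a data monitoring committee reviewing data for participant safety. If the programmer instead codes >15 without comment, the analysis departs from the prespecified definition with no record of it.

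**Working it through.** There is no sample size, power or alpha figure to reproduce here. The check is one of set inclusion, followed by an illustration of direction.

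**Step 1. Inputs, all from Section 3.0.**

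| Outcome | Range (mmol/l) |
|---|---|
| Target range (primary) | 3.9-10 |
| Euglycaemia | 3.9-7.8 |
| Hypoglycaemia | <3.9 |
| Hypoglycaemia, lower threshold | <2.8 |
| Hyperglycaemia | >10 |
| Severe hyperglycaemia, as written | <15 |

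**Step 2. Inclusion.** The ranges for <3.9, 3.9-7.8, 3.9-10, >10, <15 and >15 were compared on a grid from 2.0 to 25.0 mmol/l in steps of 0.1.

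- All hypoglycaemia (<3.9, and therefore <2.8) lies inside <15.
- All euglycaemia and the whole target range lie inside <15.
- The overlap of <15 with hyperglycaemia (>10) is 10.1 to 14.9, the milder part of hyperglycaemia.
- <15 is not a subset of >10.
- With the sign reversed, >15 is a subset of >10, as the label requires.

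**Step 3. Direction.** For any glucose trace, % time <15 = 100 − % time ≥15. For two arms A and B, the difference in the outcome as written is

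(100 − A≥15) − (100 − B≥15) = −(A≥15 − B≥15).

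The difference keeps its size and changes its sign. This is an identity and needs no data.

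**Step 4. Illustration.** The document gives no distribution of glucose or time above 15, so these figures are assumptions.

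- Simple case: time at or above 15 falls from 8% on sensor-augmented pump to 4% on the artificial pancreas. As written, 100 − 8 = 92% and 100 − 4 = 96%.
- Normal glucose distributions, with % time <15 = Φ((15 − mean)/SD):

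| Assumed profile | (15 − mean)/SD | <15, as written | >15 | >10 | 3.9-10 |
|---|---|---|---|---|---|
| Worse control: mean 9.0, SD 3.5 | 6.0/3.5 = 1.71 | 95.7% | 4.3% | 38.8% | 54.0% |
| Better control: mean 8.3, SD 3.0 | 6.7/3.0 = 2.23 | 98.7% | 1.3% | 28.5% | 64.3% |

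Going from worse to better control, the outcome as written rises by 98.7 − 95.7 = 3.0 percentage points, while true time above 15 falls by 4.3 − 1.3 = 3.0. The literal definition also puts 95.7% of time in the severe category when only 38.8% is hyperglycaemic at all, which is impossible for a subset.

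**Step 5. Could this be a fault in reading the PDF?** Unlikely. The > sign is intact in the line immediately above and in Section 2.0, and the < sign is correct in both hypoglycaemia lines. The source file should still be looked at.

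**The case against.** The strongest reply is that this is a typing slip with an obvious intent. The item is called severe hyperglycaemia, it follows hyperglycaemia above 10, and the two items echo the nested hypoglycaemia pair (<3.9, then <2.8). A literal calculation would probably give values above 90% beside a much smaller time above 10, and a data monitoring committee that includes a statistician and a diabetologist would be likely to notice. The error is also recoverable: the sensor data are unchanged, the outcome can be recalculated at any time, and because only the sign of the difference flips, a two-sided paired test gives the same p-value. It affects one of 19 secondary outcomes, and high glucose is also measured by time above 10, HBGI, mean sensor glucose, area under the curve and ketoacidosis.

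All of this stands, and it limits the seriousness of the point. Nothing in the document shows that the error has reached any code or report. But none of it makes the definition correct. Relying on someone to notice is a weaker safeguard than a correct prespecified threshold, and a silent correction in code would leave the analysis at odds with the plan.

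**Conclusion.** The definition is wrong as written. It contradicts its own label and the plan's own range for hyperglycaemia, and nothing elsewhere in the document puts it right. Followed literally, it yields the complement of time at or above 15 mmol/l and reverses the direction of benefit. That conclusion rests only on the ranges in Section 3.0; the percentages above are illustrations and do not estimate what this trial would show. The likely explanation is a typographical slip for >15. The effect is confined to one secondary outcome. The primary outcome, both hypotheses and the power calculation are untouched. It should be corrected, but it does not threaten the trial's main conclusion.

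**What to change.** In the secondary outcomes of Section 3.0, change the definition to the percentage of time with glucose >15 mmol/l. State how a reading of exactly 15.0 mmol/l is classed; a strict inequality would match the way the plan treats 10 mmol/l, which belongs to the target range and not to hyperglycaemia. Make the change before analysis code is written or the metric is used in an interim review, and check anything already derived from this list, such as a registry entry or code list, for the same sign. The cost is one character and a short note on the boundary. No data collection, visit or sample size is affected.

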4.0 Data

During the course of the study visits some data will be stored on laptop computers, not connected to the Internet, for later statistical analysis. These data will be coded and non-identifiable. Any identifiable participant data collected at screening will be stored in a locked filing cabinet in a secure room in Imperial College Healthcare NHS Trust. Only the clinical research team will have access to the filing cabinet.

Electronic data will be stored by subject number only on NHS and Imperial College desktop computers which are in the same locked room. Laptop computers may be used during the visits for portability and convenience. At the end of each visit the anonymised data will be transferred immediately to the secure NHS and Imperial College computers and will be deleted from the laptop.

All data will be stored in an anonymised form by using study numbers for identification of participants. The NHS code of confidentiality will be followed and all activity will meet the requirements of the data protection act.

Only members of the clinical research team and those responsible for direct care will have access to participants' data during the study. The data generated by the study will be analysed by the research team including the engineering team from Imperial College. The analysis will be on anonymised data and will take place in Imperial College Healthcare NHS Trust and in Imperial College academic buildings, both in the Faculty of Medicine and in the Faculty of Engineering. Fully anonymised data may be shared with future collaborators to support further development.

Electronic data transmission and storage

Data security and privacy will be a priority whilst dealing with data obtained throughout the study. During the clinical study anonymised clinical data (real-time continuous glucose data and insulin doses recommended by the BiAP and ABC4D algorithms) will be automatically transmitted between components of the BiAP system and stored locally on the BiAP device. In addition, RT-CGM data will be available to the study team using a CE marked smartphone application (Dexcom Follow App) to allow remote supervision of the artificial pancreas functioning. All data will be stored and protected against non-authorised access; transmission of data will be secured; only authorised users will have access to stored data. Authorised users will include the clinical and engineering study team members and individual participants will have access to their own data.

Direct Access to Source Data/Documents

The investigator(s)/institution(s) will permit trial-related monitoring, audits, IRB/IEC review, and regulatory inspection(s), providing direct access to source data/documents.

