The safety and feasibility of the ABC4D has been evaluated pilot clinical study over 6 weeks in 10 adult participants with T1DM. The clinical outcomes from the pilot study showed that ABC4D is safe and maintains glycaemic control with a trend suggesting improvement in post-prandial hypoglycaemia and overall glucose outcomes (20). A separate analysis of the case parameters used in ABC4D showed that the alcohol and exercise parameters were most frequently used suggesting a clinical benefit in terms of improving post-prandial hypoglycaemia (21). The usability and acceptability of the system architecture was favourable with 8 out of 10 users trusting the advice generated and 9 out of 10 happy to use ABC4D (22). A powered randomised controlled trial over 6 months is currently underway to assess whether the ABC4D system is superior to a non-adaptive bolus calculator.

The components of the closed-loop insulin delivery system

The complete device used in this protocol comprises a commercial continuous subcutaneous glucose sensor (Dexcom G5 CGM system), the BiAP control algorithm implemented in a low-power handheld device (developed by the Imperial Diabetes Technology team), the ABC4D adaptive bolus calculator algorithm in a smartphone platform (developed by the Imperial Diabetes Technology team) and a commercial continuous subcutaneous infusion pumps (Tandem T-slim) to provide glucose control. Fig 1 gives an overview of the complete system architecture. If participants already have intraperitoneal (IP) access (DiaPort) then the insulin will be delivered via the intraperitoneal route in accordance with these participants' standard care.

Glucose sensor

The glucose sensor that will be used throughout the clinical validation studies is a CE marked and MHRA approved device commercially available (Dexcom G5 Mobile CGM system). Subcutaneous sensors sit just under the skin and sample interstitial fluid using an enzyme electrode. A small voltage is applied across the sensor and a current is fed back to the sensor instrumentation. This current is proportional to the glucose concentration in interstitial fluid and is calibrated against blood glucose a minimum of 12 hourly.

BiAP algorithm in a low-power handheld device As outlined above

ABC4D adaptive bolus calculator algorithm in a smartphone platform As outlined above

Insulin infusion pump

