The day-to-day management of the study will be co-ordinated by [name] and the rest multidisciplinary research team. The chief investigator or other senior researchers will chair weekly research meetings and monthly data reviews. Annual reports to the funder and sponsor will be written and submitted. A data monitoring committee, including statistical expertise, a lay member with diabetes and a consultant diabetologist not involved with the study, will be established to provide overview of the clinical study. The data monitoring committee will meet regularly to review and evaluate the study data for participant safety, study conduct and progress.

Publication Policy

The study will be registered on the clinicaltrials.gov system and results will be disseminated by peer reviewed scientific journals, internal report, conference presentation and publication on websites. No identifiable personal data will be published. All anthropometry and personal clinical data will be expressed as mean/ median and spread of the population in the study. All participants will be informed of the results by letter at the conclusion of the study and details of any publications that arise from the study will be disseminated to participants.

References

- Thabit, H. & Hovorka, R. Coming of age: the artificial pancreas for type 1 diabetes. Diabetologia (2016) 59: 1795. doi:10.1007/s00125-016-4022-4

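### No masking of the outcome analysis is described, although the analysts include the engineering team of the institution that developed the devices; a re-keyed, arm-coded CGM file would reduce the risk cheaply

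*Combined protocol and SAP*

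**What the plan says.** - **Who analyses.** Section 4.0 (Data): "The data generated by the study will be analysed by the research team including the engineering team from Imperial College". Part of this work takes place in the Faculty of Engineering.
- **Who developed the devices.** Section 1.0, on the components of the closed-loop system, lists "the BiAP control algorithm implemented in a low-power handheld device (developed by the Imperial Diabetes Technology team") and credits the same team with ABC4D. Section 2.0 makes the evaluation of these two algorithms the main objective.
- **Blinding.** Section 2.0 (Methodology): "Randomised controlled cross-over open label study".
- **What is hidden.** Section 4.0: "The analysis will be on anonymised data", and "All data will be stored in an anonymised form by using study numbers for identification of participants". This conceals the person. Nothing is said about concealing the arm.
- **What is left open.** Section 3.0 names a paired t test, but only for sample size. Missing, unused or spurious data are judged individually and "may be ignored, withdrawn or the visit may be removed from the analysis with appropriate justification adjudicated by the Principal Investigator". No numeric rule is given.
- **Interim looks.** Section 3.0 also plans an analysis after each visit covering efficacy and safety, without naming who does it.
- **Who sees data during the trial.** Section 4.0 states: "Only members of the clinical research team and those responsible for direct care will have access to participants' data during the study". The later subsection on electronic transmission and storage names engineering team members among the authorised users of stored data, which include the insulin doses recommended by the algorithms. These two statements need to be reconciled.
- **Independent oversight.** Section 6.0 (Study Management): "A data monitoring committee, including statistical expertise", will be set up. Its stated task is safety, conduct and progress, not the outcome analysis.

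**The concern.** Participants and staff can hardly be masked to these devices, but those who clean the data and run the comparisons can be. The plan describes no such step, and it leaves open how to treat sensor gaps, minimum data, partial periods and transformation, and which visits to drop. Each choice can shift time in range a little. If the people choosing can tell which arm gains, a modest positive result is open to the criticism that the analysis was settled with the answer in view. That criticism carries more weight when the analysts come from the institution whose devices are being judged.

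**Working it through.** **1. Reading the sections together.** The plan gives no figure for this point, so the main check is textual. Section 4.0 puts the engineering team among the analysts. Section 1.0 places development of both algorithms at the same institution. Section 2.0 makes the trial open label. Study numbers hide identity only. Stored insulin recommendations would reveal the arm to anyone who reads them. No masked analyst, arm code, separate outcome statistician or freeze of the analysis is described.

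**2. How much room a small shift has (illustration).** Inputs from section 3.0: n = 20, SD 9.9, an anticipated difference of 6 points between BiAP/ABC4D and BiAP/fixed bolus, and three pairwise comparisons. Assumptions: 9.9 is the SD of paired differences, and the unspecified correction is Bonferroni, 0.05/3 = 0.0167 two-sided.

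- SE = 9.9/√20 = 2.21.
- Critical t (19 df, 0.0167) = 2.63 (2.625 before rounding).
- Smallest significant estimate = 2.625 × 2.214 = 5.81 points.
- Estimate 6: t = 6/2.214 = 2.71, p = 0.014 (significant).
- Estimate 5: t = 5/2.214 = 2.26, p = 0.036 (not significant).
- Estimates 12 and 11: t = 5.42 and 4.97, p about 0.00003 and 0.00009 (no change of conclusion).

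**3. Sensitivity to the reading of 9.9.** The plan claims 90% power with 20 participants for a 12-point difference. With 9.9 as the SD of differences, power at 0.0167 is 99.5% and 13 participants would suffice. The claim is approached if 9.9 is a per-period SD with zero correlation: the SD of differences is then 9.9 × √2 = 14.0, and the required number is 19 by the normal approximation or 22 by the t distribution. On that reading SE = 14.0/√20 = 3.13 and the smallest significant estimate is 2.625 × 3.13 = 8.2 points, above the anticipated 6. The 5.8-point figure therefore depends on how 9.9 is read.

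**4. What knowledge of the arm can do through exclusions.** Simulation of one paired comparison with no true effect: n = 20, SD of differences 9.9, 100,000 runs. Either the k least favourable participants are dropped, or the k most extreme are dropped without regard to direction. Removing one visit takes that participant out of a paired comparison, so section 3.0 permits exclusions of this kind.

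| Dropped | Mean shift, direction known | False favourable result at 0.05 | At 0.05/3 |
|---|---|---|---|
| 0 | 0 | 2.5% | 0.8% |
| 1 | +1.0 | 7.5% | 3.1% |
| 2 | +1.8 | 15.5% | 7.4% |
| 3 | +2.6 | 25.9% | 14.1% |

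When direction is ignored, the mean shift stays near 0 and the false favourable rate near 2.7% (0.05) or 0.9% to 1.0% (0.05/3). This is an extreme case of selection. It shows what masked adjudication can prevent, not what is expected to happen.

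**The case against.** **The outcome is objective.** Time in range is measured by a device and computed by formula. This stands: measurement is not the weak point. The exposure lies in which data enter the formula and how the result is analysed.

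**Prespecification is the real cure.** Fixed rules for gaps, minimum data and partial periods would close most of the open choices. This largely stands, and the rules belong in the fix. Some individual judgement would remain under section 3.0, and masking protects that part.

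**Recoding the arm alone would not mask.** In a crossover, study number plus period identifies the arm to anyone who knows one participant's sequence, and calendar dates do the same. If the codes are common to all participants, one decoded sequence opens all of them. The team starts each arm at the visits, and engineers give 24-hour support. This stands: identifiers must be re-keyed, and the interim looks must be kept away from the masked analysts.

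**The 6-versus-5 example sits on the threshold.** It does, and a 1-point shift would not matter near 12 points. No analysis choice is shown to move time in range by a full point. The example is an illustration only.

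**Readings that go too far.** A reader might infer that the analysts work with arms revealed; section 4.0 is silent on arm labels. A reader might infer that the analysing engineers are the developers themselves; that is a strong inference from the shared institution, but it is not stated. Nothing in the documents suggests misconduct.

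**Conclusion.** The point holds as a cheap improvement. In an open-label trial of the institution's own devices, the plan includes its engineering team among the analysts, describes no masking of the analysis, and leaves exclusions and several analysis choices to judgement. Those choices can therefore be made with knowledge of the arm.

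The size of any bias cannot be derived from the documents. The narrow margin of 0.19 points (6 − 5.81) rests on two assumptions, that 9.9 is the SD of paired differences and that the correction is Bonferroni. The simulation covers the exclusion route only. No stated sample size, alpha or power changes.

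A reader might also conclude that an arm-coded file would eliminate the bias route. It would not: traces may give some arms away, outcomes such as time in closed-loop control reveal the arm by nature, and behaviour during an open-label trial is untouched.

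**What to change.** State in section 4.0 that time in range and the other CGM-derived outcomes are cleaned and analysed under these conditions:

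1. **File.** It holds sensor glucose only, with a new random participant ID (not the study number), a scrambled arm code, the period number, and time as day and clock time since the period started. It contains no calendar dates, loop state or insulin records.
2. **Key.** It is held outside the analysis group, for example by the statistical member of the data monitoring committee.
3. **Rules.** Handling of sensor gaps, minimum data and partial periods is fixed beforehand.
4. **Exclusions.** The Principal Investigator's adjudication under section 3.0 is done on this masked file.
5. **Freeze.** The three comparisons are run and archived before the key is opened.
6. **Interim looks.** Per-visit analyses that show arms are kept apart from those who run the masked analysis, for example with the data monitoring committee.
7. **Device logs.** Unmasked logs are used only for device-performance outcomes.

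Reconcile the two statements in section 4.0 on who may see data during the study.

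The cost is protocol wording, a short recoding script, a short delay before unmasked results, and reorganisation of the interim looks. No extra staff should be needed, since the committee already includes statistical expertise. The remaining weakness is that some arms may be guessed from the glucose traces.
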